5. STUDY TREATMENT INFORMATION

For this study, the term "study treatment" refers to the combination of nanatinostat and valganciclovir in Phase 1b and nanatinostat and valganciclovir with or without pembrolizumab in Phase 2 only.

5.1. Nanatinostat

5.1.1. Dosage Form, Composition, and Packaging

Nanatinostat is available as 10 mg tablets. Instructions for requesting and receiving nanatinostat from the Sponsor will be included in the Study Manual.

Nanatinostat (VRx-3996) is a hydroxamic acid-based HDAC inhibitor (Moffat 2010). As is typical of this class, the structure of nanatinostat has 3 main components: a hydroxamic acid that coordinates with the Zn²⁺ ion in the active pocket of the enzyme, a spacer (azabicyclo pyrimidine) that fills out the narrow channel of the binding site, and a hydrophobic head group, amino methyl(fluoroquinoline), that interacts with the rim surrounding the pocket of the active site.

Nanatinostat is an off-white to pale orange solid with a molecular formula of C₂₀H₁₉FN₆O₂, and a molecular weight of 394.41 Da. The structural formula is presented in Figure 4.

Figure 4: Structural Formula and Key Features of Nanatinostat

Nanatinostat film-coated immediate-release (IR) 10 mg tablets consisting of the active nanatinostat (VRx-3996), and inactive excipients (ie, mannitol, microcrystalline cellulose, croscarmellose sodium, and sodium stearyl fumarate). The tablets are film coated with non-functional Opadry II white.

All inactive ingredients in the drug product meet compendial requirements of the United States Pharmacopeia and/or National Formulary.

5.1.2. Nanatinostat Study Drug Storage

Nanatinostat should be stored at controlled room temperature (20 to 25°C, 68 to 77°F) in a secure location. Excursions are permitted to 15°C to 30°C (59°F to 86°F). Once the bottle seal is broken, bottles should be stored tightly capped.

5.1.3. Nanatinostat Administration

All patients will receive nanatinostat orally once or twice daily (at breakfast or breakfast and lunch, respectively) on Days 1 to 4 per week (ie, 4 days on, 3 days off) or Days 1 to 7 per week. Following the completion of the 28-day Cycle 1, patients will continue dosing in 21-day cycles until discontinuation as described in Section 7.3.3.

Because valganciclovir tablets should be taken with food per prescribing information (Valcyte [valganciclovir] Prescribing Information, 2021), patients should be instructed to take both valganciclovir and nanatinostat with food and not fasting.

See Appendix 1 for medications to be used with caution with nanatinostat.

5.2. Valganciclovir

Valganciclovir is a cytomegalovirus nucleoside analogue DNA polymerase inhibitor.

5.2.1. Dosage Form, Composition, and Packaging

Valganciclovir is available as 450 mg tablets packaged in bottles.

Valganciclovir hydrochloride is a white to off-white solid with a molecular formula of C_{14} H_{22} N_6 O_5 . HCl, and a molecular weight of 390.82 g/mol. The structural formula is presented in Figure 5.

Figure 5: Valganciclovir Hydrochloride Structural Formula

Valganciclovir tablets manufactured by Viracta or commercially sourced will be provided to the investigational sites. Valganciclovir film-coated IR 450 mg tablets consist of the active valganciclovir (as hydrochloride) and inactive excipients (ie, microcrystalline cellulose, povidone, crospovidone, and magnesium stearate). The tablets are film coated with a non-functional coating.

Instructions for requesting and receiving valganciclovir will be included in the Study Manual.

5.2.2. Valganciclovir Study Drug Storage

Valganciclovir should be stored at controlled room temperature (20°C to 25°C, 68°F to 77°F) in a secure location. Excursions are permitted to 15°C to 30°C (59°F to 86°F). Once the bottle seal is broken, bottles should be stored tightly capped.

5.2.3. Valganciclovir Administration

The daily oral dose of valganciclovir is 900 mg once daily; 900 mg twice daily for 21 days (at breakfast and dinner) followed by a subsequent dose reduction to 900 mg once daily; or 450 mg twice daily at breakfast and lunch, in combination with nanatinostat. Following the completion

of the 28-day Cycle 1, patients will continue to receive the combination of nanatinostat and valganciclovir in 21-day cycles until discontinuation as described in Section 7.3.3.

Valganciclovir doses should be adjusted for patients who develop an elevated creatinine while on study (see Section 5.6).

Because valganciclovir tablets should be taken with food per prescribing information (Valcyte [valganciclovir] Prescribing Information, 2021), patients should be instructed to take both valganciclovir and nanatinostat with food and not fasting.

All dosages of study treatment prescribed and dispensed to the patient, and all dose adjustments made during the study, must be accurately recorded in the eCRFs.

5.3. Pembrolizumab

Pembrolizumab is a humanized monoclonal PD-1 inhibitor antibody (IgG4/kappa isotype with a stabilizing sequence alteration in the Fc region) produced in Chinese hamster ovary cells by recombinant DNA technology.

Pembrolizumab is available for injection in 100 mg/4 mL (25 mg/mL) colorless to slightly yellow solution in a single-dose vial and will be provided from commercial sources. Instructions for pembrolizumab will be included in the Study Manual.

5.3.1. Pembrolizumab Study Drug Storage

Pembrolizumab solution (injection) will be supplied in cartons containing either one or two 100 mg/4 mL (25 mg/mL) vials. Vials should be stored refrigerated (2°C to 8°C, 36°F to 46°F) in the original carton to protect from light.

As described in Section 5.3.2, pembrolizumab solution is diluted in an IV bag of sodium chloride or glucose. The diluted pembrolizumab solution may be stored at room temperature (20°C to 25°C, 68°F to 77°F) for no more than 6 hours from the time of dilution (this time includes room temperature storage of the diluted solution and the duration of infusion) and refrigerated for no more than 96 hours from the time of dilution. If refrigerated, the IV solution should come to room temperature prior to administration.

5.3.2. Pembrolizumab Administration

Prior to administration, pembrolizumab solution is transferred into an IV bag of sodium chloride 9 mg/mL (0.9%) or glucose 50 mg/mL (5%). The diluted solution is mixed by gentle inversion; the solution should not be shaken. The final concentration of the diluted solution is between 1 mg/mL to 10 mg/mL. The infusion solution is administered by IV over 30 minutes. Pembrolizumab should not be co-administered with other drugs through the same infusion line.

The dose of pembrolizumab is 200 mg IV every 3 weeks (Section 5.5.1). On treatment days, pembrolizumab should be administered within an hour following nanatinostat and valganciclovir (nanatinostat and valganciclovir are administered first). Additional administration information is provided in the pembrolizumab prescribing information (Keytruda [pembrolizumab] Prescribing Information, 2023).

5.3.3. Sequence of Study Drug Administration

The intermittent weekly dosing sequence for nanatinostat in combination with valganciclovir in Phase 1b dose levels 1 through 3 (defined in Table 4) is presented in Figure 6.

For patients receiving divided dosing of nanatinostat and single dosing of valganciclovir (dose levels 4 and 5 defined in Table 4), the first dose of nanatinostat and the only dose of valganciclovir will be taken at approximately breakfast time; the second dose of nanatinostat 4 hours later will be taken at approximately lunch time. The sequence for intermittent divided dosing of nanatinostat only is presented in Figure 7.

For the first 21 days of Cycle 1, patients receiving divided dosing of both nanatinostat and valganciclovir (dose levels 6 and 7 defined in Table 4) will take the first dose of nanatinostat and valganciclovir at approximately breakfast time, the second dose of nanatinostat 4 hours later at approximately lunch time, and then the second dose of valganciclovir in the evening at approximately dinner time on Days 1 to 4 per week. Patients will continue to receive divided dosing of valganciclovir at breakfast and dinner on Days 5 to 7 per week. Following the first 21 days, these patients will continue to receive divided dosing of nanatinostat on Days 1 to 4 per week, but subsequent valganciclovir dosing will be reduced to once daily at breakfast. The sequence for divided dosing of both nanatinostat and valganciclovir is presented in Figure 8.

For patients receiving split daily dosing of both nanatinostat and valganciclovir (dose levels 8 through 13 defined in Table 4), the first dose of nanatinostat and valganciclovir will be taken at approximately breakfast time and the second dose of nanatinostat and valganciclovir will be taken 4 hours later at approximately lunch time on Days 1 to 7. The sequence for split daily dosing of both nanatinostat and valganciclovir is presented in Figure 9.

The dosing sequence for nanatinostat and valganciclovir during the two dose optimization cohorts following identification of the RP2D is presented in Figure 10.

The dosing sequence for nanatinostat and valganciclovir in combination with pembrolizumab during Phase 2 is presented in Figure 10. During Cycle 1, pembrolizumab will be administered on Day 8 of the 28-day cycle. This sequence will allow for the collection of PK samples (for nanatinostat and valganciclovir) and may potentiate the efficacy of pembrolizumab based on the rationale provided in Section 1.5. The dosing sequence for nanatinostat and valganciclovir without pembrolizumab during Phase 2 is presented in Figure 9.

Note: Following Cycle 1, pembrolizumab will be administered on Day 1 of each subsequent 21-day cycle. Nanatinostat will continue to be administered on Days 1 to 4 or 1 to 7 per week and valganciclovir will be administered every day.

Figure 6: Dosing Sequence: Nanatinostat and Valganciclovir (Phase 1b Dose Levels 1 through 3)

Nanatinostat and Valganciclovir Weekly Dosing

[figure not shown]
[figure not shown]

Figure 7: Divided Dosing Sequence: Nanatinostat (Dose Levels 4 and 5)

Divided Dosing: Nanatinostat (Dose levels 4 and 5)

[figure not shown]

Dose levels defined in Table 4.

[figure not shown]
Note: If divided dosing for nanatinostat only is determined as the RP2D for Phase 2, pembrolizumab and valganciclovir dosing will not be split and will follow the sequence described in Figure 10.

Figure 8: Divided Dosing Sequence: Nanatinostat and Valganciclovir (Dose Levels 6 and 7)

Divided Dosing: Nanatinostat and Valganciclovir Cycle 1, Weeks 1 – 3 (first 21 days)

Cycle 1, Week 4 and Subsequent Cycles/Weeks

[figure not shown]
Dose levels defined in Table 4.

Note: If divided dosing for nanatinostat and valganciclovir is determined as the RP2D for Phase 2, pembrolizumab dosing will not be split and will follow the sequence described in Figure 10.

Figure 9: Split Daily Dosing Sequence: Nanatinostat and Valganciclovir (Dose Levels 8 through 13)

Split Daily Dosing: Nanatinostat and Valganciclovir

Breakfast: Nanatinostat and Valganciclovir Lunch: Nanatinostat and Valganciclovir

[figure not shown]

Dose levels defined in Table 4.

[figure not shown]
Note: refer to Figure 6 through Figure 8 if the dosing schedule returns to intermittent nanatinostat dosing.

Figure 10: Dosing Sequence: Nanatinostat, Valganciclovir, and Pembrolizumab – Phase 2 Dose Expansion

Nanatinostat, Valganciclovir, and Pembrolizumab – Cycle 1 Only

Nanatinostat, Valganciclovir, and Pembrolizumab –Subsequent Cycles

Note: refer to Figure 6 through Figure 8 if the confirmed RP2D returns to intermittent nanatinostat dosing. Pembrolizumab will continue to be administered as illustrated in Figure 10.

5.4. Additional Dosing Guidelines for Pharmacokinetic Sampling

In an effort to standardize food intake for the PK assessments, patients will be asked to consume one can of Ensure® meal replacement shake or equivalent, prior to the dose of study treatment (within 30 minutes) on days with pre- and post-dose PK assessments as outlined in Section 7.4.3. An Ensure equivalent is defined as any liquid nutrition that is at least 8 ounces in size containing at least 8 grams of protein and at least 6 grams of fat. Alternatively, patients may consume a light breakfast in place of consuming an Ensure or equivalent meal replacement shake. The meal should start 30 minutes before administration of valganciclovir and nanatinostat.

Note that nanatinostat and valganciclovir should be taken at the same time, including on Cycle 1 Day 1 (for divided dosing, the first doses of the day should be taken together in the morning at approximately breakfast). For patients receiving divided or split daily dosing of nanatinostat and valganciclovir (dose levels 4-13; Table 4), the 4-hour PK time point samples should be collected prior to administration of the second dose of nanatinostat (ie, at approximately lunch time). For patients receiving divided dosing of valganciclovir (dose levels 6 and 7), the 8-hour PK timepoint should be collected prior to administration of the second dose of valganciclovir (ie, at approximately dinner time).

See Appendix 1 for medications to be used with caution with nanatinostat.

5.5. Dose Escalation Guidelines

5.5.1. Provisional Dose Levels

Table 4 describes the starting doses and the provisional dose levels of nanatinostat and valganciclovir (Phase 1b) and nanatinostat and valganciclovir with pembrolizumab (Phase 2 Dose Optimization and Phase 2 Expansion) to be evaluated. The actual dose levels will be determined based on available data following a discussion with Investigators during dose-escalation teleconferences. No intrapatient dose escalation will be permitted in the Phase 1b dose escalation.

Table 4: Phase 1b: Dose Levels – Nanatinostat and Valganciclovir

Dose Level	Nanatinostat Oral Dose on Days 1-4/Week	Valganciclovir Oral Dose Daily
-1	10 mg once daily	900 mg once daily
1	20 mg once daily	900 mg once daily
2	30 mg once daily	900 mg once daily
3	40 mg once daily	900 mg once daily
4	20 mg and 10 mg divided dose	900 mg once daily
5	20 mg twice daily	900 mg once daily
6	10 mg twice daily	900 mg twice daily × 21 days, then once daily
7	20 mg and 10 mg divided dose	900 mg twice daily × 21 days, then once daily
	Nanatinostat Oral Dose Twice Daily on Days 1-7/Week	Valganciclovir Oral Dose Twice Daily on Days 1-7/Week
8 ^a	20 mg and 10 mg divided dose	450 mg twice daily

9ª	20 mg and 20 mg divided dose 450 mg twice daily			
10 ^a	30 mg and 20 mg divided dose	450 mg twice daily		
11ª	30 mg and 30 mg divided dose	450 mg twice daily		
12ª	40 mg and 30 mg divided dose	450 mg twice daily		
13ª	40 mg and 40 mg divided dose	450 mg twice daily		

DLT = dose-limiting toxicity; RP2D = recommended Phase 2 dose

Guidelines for Dose Escalation 5.5.2.

During the DLT evaluation window of both phases of the study, patients who permanently discontinue study treatment prior to receiving 75% of the planned number of nanatinostat and valganciclovir doses or 2 pembrolizumab doses due to reasons other than study drug-related toxicity will not be considered evaluable for DLT and may be replaced.

Phase 1b

IND 154400

The RP2D of nanatinostat in Phase 1b will be defined as the highest dose administered with standard daily doses of valganciclovir (900 mg once or 450 mg twice daily) for which <33% of patients experience a DLT (defined in Section 5.5.3) during the first treatment cycle (28 days) up to a maximum daily dose of 80 mg administered with food either as a single daily dose administered intermittently (Days 1 to 4 per week) or as a split dose twice daily administered continuously (Days 1 to 7 per week). In addition to toxicity, PK, antitumor activity, plus pharmacodynamic markers of disease response (plasma EBV DNA levels) will be considered in the final determination of the RP2D in consultation with the SMC. Dose escalation rules during Phase 1b are presented in Table 5.

Table 5: Phase 1b Dose Escalation Rules for Nanatinostat in Combination with Valganciclovir*

Dose level	Outcome	Action		
-1 Nanatinostat 10 mg daily,	If none of the first 3 patients experiences a DLT	Proceed to expansion cohorts.		
Days 1-4/wk	If 1 of 3 patients experiences a DLT	Enroll 3 more patients into dose level -1		
Valganciclovir 900 mg daily	If 1 of 6 patients experiences a DLT	Declare dose level -1 to be RP2D		
	If ≥2/6 patients experience a DLT	Convene safety review to discuss next steps.		
1 Starting dose	If none of the first 3 patients experiences a DLT	Proceed to dose level 2		
Nanatinostat 20 mg daily,	If 1 of 3 patients experiences a DLT	Enroll 3 more patients into dose level 1		
Days 1-4/wk	If 1 of 6 patients experiences a DLT	Proceed to dose level 2		
Valganciclovir 900 mg daily	If ≥2/6 patients experience a DLT	Decrease nanatinostat to dose level -1 and proceed.		
Nanatinostat 30 mg daily,	If none of the first 3 patients experiences a DLT	Proceed to dose level 3		
Days 1-4/wk	If 1 of 3 patients experiences a DLT	Enroll 3 more patients into dose level 2.		
Valganciclovir 900 mg daily	If 1 of 6 patients experiences a DLT	Proceed to dose level 3.		
	If ≥2/6 patients experience a DLT	Declare dose level 1 the RP2D.		

a: Dose levels 9, 11, and 13 are planned dose levels, while dose levels 8, 10, and 12 are planned provisional dose levels for stepping up or down based on the DLT profile to potentially better determine the RP2D. See Table 5 for further details.

Dose level	Outcome	Action			
3 Nanatinostat 40 mg daily,	If none of the first 3 patients experiences a DLT	Proceed to dose level 6.			
Days 1-4/wk	If 1 of 3 patients experiences a DLT	Enroll 3 more patients into dose level 3.			
Valganciclovir 900 mg daily	If 1 of 6 patients experiences a DLT	Proceed to dose level 6.			
· · · · · · · · · · · · · · · · · · ·	If ≥2/6 patients experience a DLT	Proceed to dose level 4.			
4 Nanatinostat 20 mg + 10 mg	If none of the first 3 patients experiences a DLT	Declare 30 mg nanatinostat the RP2D*			
divided dose, Days 1-4/wk	If 1 of 3 patients experiences a DLT	Enroll 3 more patients into dose level 4.			
Valganciclovir 900 mg daily	If 1 of 6 patients experiences a DLT	Declare 30 mg nanatinostat the RP2D*			
waganere vir you ing unity	If ≥2/6 patients experience a DLT	Declare dose level 2 the RP2D.			
5 Nanatinostat 20 mg BID,	If none of the first 3 patients experiences a DLT	Declare 40 mg nanatinostat the RP2D*			
Days 1-4/wk	If 1 of 3 patients experiences a DLT	Enroll 3 more patients into dose level 5.			
Valganciclovir 900 mg daily	If 1 of 6 patients experiences a DLT	Declare 40 mg nanatinostat the RP2D*			
	If ≥2/6 patients experience a DLT	Declare dose level 3 the RP2D.			
6 Nanatinostat 10 mg BID,	If none of the first 3 patients experiences a DLT	Proceed to dose level 7.			
Days 1-4/wk	If 1 of 3 patients experiences a DLT	Enroll 3 more patients into dose level 6.			
Valganciclovir 900 mg BID for	If 1 of 6 patients experiences a DLT	Proceed to dose level 7.			
21 days, then daily	If ≥2/6 patients experience a DLT	Proceed to dose level 5.			
7 Nanatinostat 20 mg + 10 mg	If none of the first 3 patients experiences a DLT	Proceed to dose level 9.			
divided dose, Days 1-4/wk	If 1 of 3 patients experiences a DLT	Enroll 3 more patients into dose level 7.			
Valganciclovir 900 mg BID for 21 days, then daily	If 1 of 6 patients experiences a DLT	Proceed to dose level 8 if it has not been previously enrolled, otherwise declare dose level 7 the RP2D.			
	If ≥2/6 patients experience a DLT	Step down to dose level 6 and enroll a total of 6 patients there. Alternatively, declare dose level 6 the RP2D if it has already enrolled 6 patients.			
8 Nanatinostat 20 mg + 10 mg divided dose, Days 1-7/wk	If none of the first 3 patients experiences a DLT	Proceed to dose level 9 if it has not been previously enrolled, otherwise declare dose level 8 the RP2D and expand dose level 8 to 6 patients to confirm RP2D determination.			
Valganciclovir 450 mg twice	If 1 of 3 patients experiences a DLT	Enroll 3 more patients into dose level 8.			
daily	If 1 of 6 patients experiences a DLT	Proceed to dose level 9 if it has not been previously enrolled, otherwise declare dose level 8 the RP2D.			
	If ≥2 patients experience a DLT	Step down to dose level 7 and enroll a total of 6 patients there. Alternatively, declare dose level 7 the RP2D if it has already enrolled 6 patients.			
9 Nanatinostat 20 mg + 20 mg	If none of the first 3 patients experiences a DLT	Proceed to dose level 11.			
divided dose, Days 1-7/wk	If 1 of 3 patients experiences a DLT	Enroll 3 more patients into dose level 9.			
Valganciclovir 450 mg twice daily	If 1 of 6 patients experiences a DLT	Proceed to dose level 10 if it has not been previously enrolled, otherwise declare dose level 9 the RP2D.			
	If ≥2 patients experience a DLT	Step down to dose level 8 and enroll a total of 6 patients there. Alternatively, declare dose level 8 the RP2D if it has already enrolled 6 patients.			
Nanatinostat 30 mg + 20 mg divided dose, Days 1-7/wk	If none of the first 3 patients experiences a DLT	Proceed to dose level 11 if it has not been previously enrolled, otherwise declare dose level 10 the RP2D and expand dose level 10 to 6 patients to confirm RP2D determination.			

Dose level	Outcome	Action			
Valganciclovir 450 mg twice	If 1 of 3 patients experiences a DLT	Enroll 3 more patients into dose level 10.			
daily	If 1 of 6 patients experiences a DLT	Proceed to dose level 11 if it has not been previously enrolled, otherwise declare dose level 10 the RP2D.			
	If ≥2 patients experience a DLT	Step down to dose level 9 and enroll a total of 6 patients there. Alternatively, declare dose level 9 the RP2D if it has already enrolled 6 patients.			
11 Nanatinostat 30 mg + 30 mg	If none of the first 3 patients experiences a DLT	Proceed to dose level 13.			
divided dose, Days 1-7/wk	If 1 of 3 patients experiences a DLT	Enroll 3 more patients in dose level 11			
Valganciclovir 450 mg twice daily	If 1 of 6 patients experiences a DLT	Proceed to dose level 12 if it has not been previously enrolled, otherwise declare dose level 11 the RP2D.			
	If ≥2 patients experience a DLT	Step down to dose level 10 and enroll a total of 6 patients there. Alternatively declare dose level 10 the RP2D if it has already enrolled 6 patients.			
Nanatinostat 40 mg + 30 mg divided dose, Days 1-7/wk	If none of the first 3 patients experiences a DLT	Proceed to dose level 13 if it has not been previously enrolled, otherwise declare dose level 12 the RP2D and expand dose level 12 to 6 patients to confirm RP2D determination.			
Valganciclovir 450 mg twice	If 1 of 3 patients experiences a DLT	Enroll 3 more patients into dose level 12.			
daily	If 1 of 6 patients experiences a DLT	Proceed to dose level 13 if it has not been previously enrolled, otherwise declare dose level 12 the RP2D.			
	If ≥2 patients experience a DLT	Step down to dose level 11 and enroll a total of 6 patients there. Alternatively, declare dose level 11 the RP2D if it has already enrolled 6 patients.			
Nanatinostat 40 mg + 40 mg divided dose, Days 1-7/wk	If none of the first 3 patients experiences a DLT	Declare dose level 13 the RP2D and expand dose level 13 to 6 patients to confirm RP2D determination			
77.1 . 1 . 450	If 1 of 3 patients experiences a DLT	Enroll 3 more patients into dose level 13.			
Valganciclovir 450 mg twice daily	If 1 of 6 patients experiences a DLT	Declare dose level 13 the RP2D			
duny	If ≥2 patients experience a DLT	Step down to dose level 12 and enroll a total of 6 patients there. Alternatively declare dose level 12 the RP2D if it has already enrolled 6 patients.			

^{*}The RP2D referenced in this table is equivalent to a maximum tolerated dose (MTD) or maximum administered dose, but ultimate determination of the RP2D of nanatinostat will be based on the evaluation of additional parameters such as the incidence and severity of AEs, tolerability, pharmacokinetic data, antitumor activity, and plasma EBV DNA levels in consultation with the Safety Monitoring Committee.

AEs = adverse events; BID = twice daily; DLT = dose-limiting toxicity; EBV = Epstein-Barr virus; RP2D = recommended Phase 2 dose; wk = week

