5.5.3.1. Phase 1b: Nanatinostat and Valganciclovir

The DLT evaluation period is 28 days.

To be considered a DLT, an AE must meet one or more of the following criteria:

- 1. Hematologic DLTs:
 - Grade 4 neutropenia or thrombocytopenia lasting ≥7 days.
 - Grade ≥3 thrombocytopenia associated with clinically significant bleeding.
- 2. Non-hematologic DLTs:
 - Grade ≥ 3 non-laboratory toxicities despite maximum supportive therapy.
 - Grade ≥3 clinically significant laboratory abnormality for which the patient is symptomatic regardless of its duration, requires medical intervention, is not corrected within 72 hours, or leads to hospitalization.
- 3. Febrile neutropenia, defined as ANC $<1000/\text{mm}^3$ with a single temperature of >38.3 °C (101 °F) or a sustained temperature of ≥ 38 °C (100.4 °F) for more than 1 hour.
- 4. Any treatment-related toxicity that results in a dose hold of >7 consecutive days or causes the patient to discontinue treatment.
- 5. Any Grade 5 toxicity not clearly due to the underlying disease or extraneous causes
- 6. Any Hy's law case: ALT and/or AST >3 × ULN and total bilirubin >2 × ULN not explained by other causes.

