Nephritis with renal dysfunction	Grade 2 or 3 increased creatinine	Withhold ¹ . Follow guidelines for valganciclovir dose reduction in Table 7. Resume in patients with complete or partial resolution (Grades 0 to 1) after valganciclovir dose adjustment and/or corticosteroid taper
	Grade 4 increased creatinine	Permanently discontinue
Exfoliative dermatologic conditions	Suspected SJS, TEN, or DRESS	Withhold ¹
	Confirmed SJS, TEN or DRESS	Permanently discontinue
Myocarditis	Grade 2, 3 or 4	Permanently discontinue
Neurological toxicities	Grade 2	Withhold ¹
	Grade 3 or 4	Permanently discontinue
Infusion-related reactions	Grades 1 or 2	Interrupt or slow the rate of infusion
	Grades 3 or 4	Permanently discontinue

Source: Keytruda [pembrolizumab] Prescribing Information, 2023

Patients should be monitored until resolution of the toxicity. During a dose interruption, study days and procedures will continue to accrue until the end of the current cycle (see Schedule of Events in Section 6). If the dose interruption extends beyond the end of the cycle, the subsequent Cycle Day 1 will not begin until dosing has resumed. If the dose is held for more than 14 days, the Investigator should consult with the Sponsor's Medical Monitor before dosing resumes.

If a patient has multiple dose interruptions for study drug toxicity or has had to interrupt for more than 14 days, a dose reduction may be considered. Re-escalation of study drug dose may only be performed after approval by the Sponsor's Medical Monitor.

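### The DLT evaluability rule has no exception for a DLT already observed and no minimum exposure for patients who stay on treatment, so the counts behind Phase 1b escalation and the RP2D can be too low

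*Protocol*

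**What the plan says.** Protocol Section 5.5.2 sets the rule for the DLT window of both phases. It covers "patients who permanently discontinue study treatment prior to receiving 75% of the planned number of nanatinostat and valganciclovir doses or 2 pembrolizumab doses", where the stop is "due to reasons other than study drug-related toxicity will not be considered evaluable for DLT and may be replaced". Three conditions must hold together: a permanent stop, a dose shortfall and a reason other than drug toxicity. Replacement is optional; non-evaluability is not.

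The same section defines the RP2D as the highest dose "for which <33% of patients experience a DLT (defined in Section 5.5.3) during the first treatment cycle (28 days"). Table 5 turns this into counts, with rows such as "If none of the first 3 patients experiences a DLT" and "If 1 of 6 patients experiences a DLT". At level 11, two or more DLTs lead to "Step down to dose level 10 and enroll a total of 6 patients there".

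Three other provisions matter:

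- Section 5.5.3.1, criterion 4, makes this a DLT: "Any treatment-related toxicity that results in a dose hold of >7 consecutive days or causes the patient to discontinue treatment".
- Section 5.6 states: "During a dose interruption, study days and procedures will continue to accrue until the end of the current cycle". Section 5.6.3 adds that missed doses are not made up at levels 4 to 13.
- Table 7 provides for restarting both drugs after febrile neutropenia and after Grade 4 neutropenia. Febrile neutropenia is a DLT in Phase 1b, and so is Grade 4 neutropenia lasting at least 7 days. A DLT therefore need not end treatment.

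Neither Protocol Section 9.3 nor SAP Section 4.2 defines a DLT-evaluable set.

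**The concern.** DLT incidence in the 28-day window is the Phase 1b primary endpoint, and it drives Table 5. The rule can depress the count in two ways.

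(a) **A DLT can be dropped.** Suppose a patient has febrile neutropenia on Day 10, recovers, restarts, and withdraws consent on Day 19 with under 75% of doses taken. The recorded reason for stopping is not toxicity, so Section 5.5.2 makes the patient non-evaluable and replaceable. Table 5 and the RP2D definition count patients who experience a DLT, and this patient did. The two texts give different counts for the same data.

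(b) **Low exposure can count as a clean result.** A patient whose drugs are held 12 days for an unrelated illness and who then resumes has not permanently stopped, so the 75% test never applies. The window keeps running and criterion 4 does not catch the hold. The same exposure followed by a permanent stop for a non-toxicity reason would be non-evaluable.

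Both faults push the counted rate down, towards escalation.

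**Working it through.** **Consistency of the plan's own figures.** 1/6 = 16.7% is below 33%; 2/6 = 33.3% is not. Table 5 agrees with the RP2D criterion, provided the counts are right.

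**Limb (a): how long a DLT is exposed.** Planned Cycle 1 doses come from Table 4. I read the 75% as applying to each drug and assume uninterrupted dosing.

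- Levels -1 to 5: valganciclovir 28 doses, 75% = 21, reached on Day 21. Nanatinostat reaches 12 of its 16 dosing days on Day 18, so valganciclovir sets the limit.
- Levels 6 and 7: valganciclovir 2 × 21 + 7 = 49 doses, 75% = 36.75, so 37 are needed. Day 18 ends at 36, so the threshold is met on Day 19.
- Levels 8 to 13: 56 doses of each drug, 75% = 42, reached at the end of Day 21.

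Any hold, including one caused by the DLT itself, pushes these days later.

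**Limb (a): effect on a decision.** At level 11, 1 DLT in 3 brings three more patients, and a second DLT makes 2 of 6: step down to level 10. Drop one of the two and add a replacement without a DLT, and the count is 1 of 6. Table 5 then leads to level 12 if that level has not yet been used, and otherwise declares level 11 the RP2D.

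**Limb (b): exposure.** A 12-day unrelated hold on daily dosing leaves (28 − 12)/28 = 16/28 = 57%.

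**Limb (b): chance of passing a level.** Passing means 0/3, or 1/3 followed by 0/3. With true DLT rate p and full exposure:

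P(pass) = (1−p)³ + 3p(1−p)² × (1−p)³

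- p = 0.33: 0.301 + 0.444 × 0.301 = 0.434
- p = 0.40: 0.216 + 0.432 × 0.216 = 0.309

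Now let one of the first three be under-dosed, with DLT risk q:

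P(0/3) = (1−p)²(1−q); P(1/3) = 2p(1−p)(1−q) + (1−p)²q; P(pass) = P(0/3) + P(1/3) × (1−p)³

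| p | q = 0 (no risk) | q = p × 16/28 (proportional to exposure) |
|---|---|---|
| 0.33 | 0.449 + 0.442 × 0.301 = 0.582 | q = 0.189: 0.364 + 0.443 × 0.301 = 0.498 |
| 0.40 | 0.360 + 0.480 × 0.216 = 0.464 | q = 0.229: 0.278 + 0.453 × 0.216 = 0.375 |

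The presence of one such patient and both values of q are assumptions. The documents give no frequency of under-dosing and no exposure-risk relation.

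**The case against.** The strongest reply is that little is at stake now. SAP Section 4.8 says enrollment ended after the final Phase 1b dose level, an RP2D was determined and Phase 2 will not run, so no Table 5 decision remains. That stands, and it turns the remedy into a check of existing data.

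A reader might infer that a dropped DLT vanishes from the reported primary endpoint. The documents do not support this. SAP Section 4.6 runs safety analyses on all treated patients, and Section 4.6.2 lists the DLT table among them. A reader might also infer that an escalation decision was in fact affected; nothing in either document shows that.

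On limb (a), Table 5 speaks of patients, not evaluable patients, and at levels 8 to 13 the step-down trigger carries no denominator. Read literally, it would still count the DLT. That makes the fault a conflict between two provisions, which still has to be reconciled. The route is also narrow: a DLT that itself ends treatment stays evaluable, and the first scheduled scan is at Week 8, so an exit for progression by about Day 21 would not come from a planned scan. The SMC would also see the event, because the Table 5 footnote bases the final RP2D on wider data.

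On limb (b), no passage says that an under-dosed patient counts as DLT-free; this is inferred from the missing exposure minimum. Treatment-related holds of more than 7 consecutive days are already DLTs, so the gap concerns unrelated holds, missed doses and repeated short toxicity holds. The 58% and 46% figures are zero-risk worst cases, and proportional risk roughly halves the shift.

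**Conclusion.** The point holds as a fault in the written rule. Section 5.5.2 can remove an observed DLT from the escalation count, contrary to Table 5 and the RP2D definition, and it sets no exposure floor for patients who remain on treatment. No other provision corrects either gap.

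For limb (a), one patient can reverse a decision, as at level 11. For limb (b), one patient at 57% exposure among the first three raises the chance of passing from 43% to between about 50% and 58% at a true 33% rate, and from 31% to between about 38% and 46% at 40%. These figures show direction and range and are conditional on such a patient occurring. What is in question is the support for the Phase 1b escalation decisions and the RP2D, not the completeness of the SAP's DLT table.

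**What to change.** Define a DLT-evaluable set in the SAP and use it in the CSR for Phase 1b:

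1. Any patient with a DLT in the window is evaluable and never replaced, whatever the later reason for stopping.
2. A patient without a DLT is evaluable only after at least the protocol's own 75% of planned nanatinostat doses and of valganciclovir doses in the window, whether or not treatment was stopped.
3. The exception is a shortfall due to study drug-related toxicity, which leaves the patient evaluable. List these patients separately: two 6-day toxicity holds also leave 16/28 = 57%, and neither exceeds 7 days, so such a patient could otherwise count as DLT-free.

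Report DLT counts by dose level under this definition beside the counts used for escalation. State whether any patient was excluded or replaced after a DLT, or counted while under-dosed, and whether any Table 5 decision or the RP2D would change. Record how Section 5.5.2 and Table 5 were reconciled in practice.

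The cost is one SAP definition, one derivation and a review of existing dosing and DLT records. The downside is that some evaluable denominators may shrink, or a past decision may look less well supported. If nothing changes, the RP2D is better supported.
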